9 TREATMENTS

Subjects will receive tipifarnib as monotherapy in this study. In the absence of unacceptable tipifarnib related emergent toxicity or disease progression, subjects may receive treatment with tipifarnib for up to 12 months at the discretion of the Investigator. Treatment beyond 12 months may continue upon agreement of the Investigator and the Sponsor. Kura Oncology, Inc. or its designee will provide the study site with a supply of tipifarnib sufficient for the completion of the study.

All study subjects will be also eligible to receive best supportive care (BSC) defined as any standard supportive measures that are not considered a primary treatment of the disease under study, including the use of growth factors (i.e. GCSF) or blood transfusions for myelosuppression. BSC will be provided by the study sites.

9.1 Investigational Product (IP)

Tipifarnib is a small molecule being developed as a potent, selective inhibitor of FTase for the treatment of cancer and other malignancies.

9.1.1 Product Characteristics

Tipifarnib film-coated tablets for oral administration are supplied in HDPE bottles. Two strengths (100 mg and 300 mg) of tablets are provided containing either 100 or 300 mg of tipifarnib active substance, respectively. In addition to the active substance, the tablets contain

the following inactive ingredients: lactose monohydrate, maize starch, hypromellose, microcrystalline cellulose, crospovidone, colloidal anhydrous silica, and magnesium stearate. The nonfunctional, taste-masking film coatings contain hypromellose, titanium dioxide, lactose monohydrate, polyethylene glycol, and triacetin. Each strength of tablet has the same excipients but the quantitative composition is slightly different. Further information can be obtained from the current version of the Investigator's Brochure.

9.1.2 Storage and Labeling

At a minimum, the label of each bottle of tipifarnib tablets shipped to the study sites will provide the following information: batch number/lot number, study identification, required storage conditions, directions for use, and country specific required caution statements (including "New Drug – Limited by United States federal law to investigational use" language).

Tipifarnib accountability records will be maintained by the pharmacy or designated drug preparation area at the study sites. Upon receipt of tipifarnib supplies, the pharmacist or designated study site investigational drug handler will inventory tipifarnib (separately for each strength, if applicable) and complete the designated section of the shipping form. The shipping/inventory form must be sent to Kura Oncology, Inc. or its designee, as instructed.

Tipifarnib should be stored at controlled room temperature 15 to 30 C (59 to 86 F). All study supplies must be kept in a restricted access area.

9.2 Treatment Administration

Tipifarnib will be administered with food at a starting dose of 600 mg, po, bid daily on days 1-7 and 15-21 of 28-day treatment cycles.

The first study dosing (Cycle 1 Day 1) will take place in the study clinic. Tipifarnib will be administered orally with a meal in the morning and again approximately 12 hours later at approximately the same times each treatment day. Tablets should be swallowed whole with water (~8 oz. or 250 mL) but may be chewed or crushed if the Investigator deems it necessary. Use of percutaneous endoscopic gastrostomy tubes is allowed at the judgment of the Investigator. If a dose is vomited or partially vomited, it should not be replaced with a new dose.

Subjects may use proton pump inhibitors or H2 antagonists during the treatment portion of this study. However, subjects should be instructed to use antacids (magnesium or aluminum containing products) at least 2 hours before or after intake of oral study drug.

On Cycle 1 Day 1, the site will provide tipifarnib to the subject from bulk supplies. Subjects will be provided with diaries with instructions to record the date and time of each dose and asked to bring the diaries and tablet bottles to each clinic visit for subject compliance and drug accountability review by the site staff.

9.3 Treatment Assignment

Treatment at each study cohort will be conducted in an open label manner. Kura Oncology, Inc. or its designee will assign a subject number identifier and treatment cohort for each subject that is enrolled into the study. Study sites cannot enroll or start dosing the subject without receiving the assigned subject number.

The second 7-day schedule study was conducted in patients with relapsed/refractory AML (Kirschbaum 2011). Tipifarnib was administered bid on days 1–7 and days 15–21 of 28-day cycles at doses up to 1600 mg bid (Kirschbaum 2011). At the 400 mg bid dose level, a grade 5

hepatorenal failure occurred, potentially related to the study drug. There were no additional DLTs reported at 600, 800 or 1000 mg bid dose levels. At the 1200 mg bid dose level, a grade 3 creatinine elevation was seen in one patient out of 6 treated. At the 1400 mg bid dose level, one patient experienced a grade 4 hypotension and a rising grade 2 creatinine that were dose limiting, and a second patient had a rising grade 2 creatinine that resulted in treatment discontinuation and was therefore considered dose limiting. At the 1600 mg dose level, grade 3 liver function tests and a rising grade 2 creatinine were dose limiting, and in a second patient, a rapidly rising creatinine was seen and treatment stopped. As a result, the 1200 mg bid dose was established as the MTD and 7 additional patients treated. Sixteen patients were treated at the 1000 and 1200 mg dosing levels, with 3 of them experiencing complete responses. No formal responses were seen among patients treated at the lower dose levels.

Based on these data, the tipifarnib regimen to be investigated in the current study was modified to a starting dose of 900 mg, po, bid on days 1-7 and 15-21 of 28-day treatment cycles. Preliminary data from KO-TIP-001 indicate a tolerability that is broadly similar to the safety profile observed of other tipifarnib regimens in prior clinical studies which administered tipifarnib daily in a 21-day on, 7 days off treatment cycle schedule. The most common AES of tipifarnib including hematological events, gastrointestinal disturbances (nausea, vomiting and diarrhea) and fatigue have been monitorable and manageable with protocol defined assessments and management of toxicity guidance. Dose reduction to 600 mg has been able to reduce tipifarnib-related toxicity and several subjects have maintained their response and continued on treatment for over 1 year.

Given these preliminary observations and in discussion with study investigators, the starting dose has been reduced to 600 mg, po, bid on days 1-7 and 15-21 of 28-day treatment cycles as part of amendment 5 to the study protocol. In the absence of unmanageable toxicities, subjects may continue to receive tipifarnib treatment for up to 12 months in the absence of disease progression and unmanageable toxicity. Stepwise 300 mg dose reductions to control treatment-related, treatment-emergent toxicities are also included in this protocol amendment. Treatment may continue beyond 12 months upon agreement of the Investigator and Sponsor.

Ongoing subjects receiving the 21-day schedule will be allowed to switch to the 7-day schedule at the discretion of the investigator. Similarly, ongoing subjects receiving 900 mg bid will be allowed to maintain that dose or switch to 600 mg bid at the discretion of the investigator.

9.5 Dose Modification and Management of Toxicity

All subjects will begin treatment with tipifarnib at a starting dose of 600 mg bid in alternating weeks. If treatment-related, treatment-emergent AEs are observed meeting criteria for dose modification detailed further in this section, the dose level reductions summarized in Table 2 will be used.

Table 2: Tipifarnib dose levels

Dose Level	Alternate Week Schedule	
	Doses in mg (am + pm)	
Starting Dose	600 + 600	
-1	300 + 600*	
-2	300 + 300	

^{*}Depending on subject preference, the 600 mg dose may be taken in the morning or in the evening, as long as the total daily dose is 900 mg, i.e. 600 mg can be taken in the morning or evening with 300 mg taken for the other scheduled dose time. Tipifarnib should always be taken with a meal.

If treatment-related treatment-emerging CTCAE grade 4 non-hematological toxicity is observed, treatment with tipifarnib will be permanently discontinued.

If treatment-related treatment-emerging CTCAE \geq grade 3 hematological or grade 3 non-hematological toxicity is observed that cannot be managed with supportive care measures, treatment with tipifarnib will be interrupted until recovery to \leq grade 2. If recovery requires more than 4 weeks, treatment is to be discontinued. Upon recovery, tipifarnib may be restarted at the original dose or at the next lower dose level (see Table 2) at the discretion of the investigator. If grade 3 or 4 toxicity recurs, subsequent dose reductions may be conducted according to Table 2.

If treatment-related treatment-emerging CTCAE grade 2 renal toxicity is observed that cannot be managed with supportive care measures (including hydration and correction of electrolyte abnormalities, if appropriate), treatment with tipifarnib will be interrupted until recovery to \leq grade 1. Upon recovery to \leq grade 1, the subject may restart tipifarnib at their current dose level.

If treatment-related treatment-emerging CTCAE grade 2 renal toxicity recurs or if grade 3 renal toxicity is observed that cannot be managed with supportive care measures, treatment with tipifarnib will be interrupted until recovery to \leq grade 1. Additional treatment may be given at the next lower dose level (see Table 2) upon subject's recovery from toxicity. If grade 2 or 3 renal toxicity recurs, a subsequent dose reduction may be conducted. Reduced doses due to renal toxicity will not be re-escalated.

Treatment with tipifarnib should also be interrupted until recovery to grade 2 tolerable or better if treatment-related treatment-emergent CTCAE grade 2 intolerable neurological toxicity is observed. Additional treatment may be given at the next lower dose level (see Table 2) upon subject's recovery from toxicity. If grade 2 intolerable neurological toxicity recurs, a subsequent dose reduction may be conducted. Reduced doses due to neurological toxicity will not be reescalated. The occurrence of grade 3 neurological toxicity will result in permanent discontinuation of treatment.

Unless otherwise indicated (e.g. dosing discontinuation), reduced doses may be re-escalated to the original dose at the judgement of the investigator. However, subjects who experience serious adverse events or a recurrence of \geq grade 3 toxicity deemed to be related to tipifarnib will not

have their dose re-escalated following dose reduction. In addition, subjects experiencing more than one dose delay of \geq 14 days will not have their dose re-escalated.

Asymptomatic laboratory findings will not be considered dose limiting unless otherwise determined by the Investigator. A summary of dose modifications is presented in Table 3.

Table 3: Summary of Dose Modifications for Treatment Related Toxicities

Adverse Event	Management	Tipifarnib Dosing
Grade 4 Non-Hematological	Discontinue tipifarnib permanently	
≥ Grade 3 Hematological or Grade 3 Non-Hematological	Manage with BSC, including RBC or platelet transfusion. If not manageable, interrupt tipifarnib treatment until recovery to grade 2 or better.	If recovery requires more than 4 weeks, treatment is to be discontinued.
		Upon recovery to ≤ grade 2, restart tipifarnib at current dose or at the next lower dose level (see Table 2) at the judgement of the investigator.
		If the same toxicity recurs, upon recovery to ≤ grade 2, re-start tipifarnib at the next lower dose level (see Table 2). If grade 3 thrombocytopenia recurs, consider additional cycles at original dose at the judgement of the investigator
Grade 2 Renal	Manage with BSC, including hydration and correction of electrolyte abnormalities, if appropriate.	Upon recovery to ≤ grade 1, restart tipifarnib at current dose.
Grade 2 Recurrent or Grade 3 Renal	Manage with BSC, including hydration and correction of electrolyte abnormalities, if appropriate. If not manageable, interrupt tipifarnib treatment until recovery to grade 1 or better	Upon recovery to ≤ grade 1, restart tipifarnib at the next lower dose level (see Table 2). If grade 2 or 3 renal toxicity recurs, upon recovery to ≤ grade 1, re-start tipifarnib at the next lower dose level (see Table 2).
Grade 2 non-tolerable Neurological	Manage with BSC. If not tolerable, interrupt tipifarnib treatment until recovery to grade 2 tolerable or better	Upon recovery to grade 2 tolerable or better, re-start tipifarnib at the next lower dose level (see Table 2).
		If grade 2 intolerable neurological toxicity recurs, upon recovery to grade 2 tolerable or better, re-start tipifarnib at the next lower dose level (see Table 2).
Grade 3 Neurological	Discontinue tipifarnib permanently	

In exceptional circumstances, dosing delays or skipping of dosing for reasons other than the management of toxicity will be allowed at the judgement of the investigator as long as 50% of the total dose is maintained in a given cycle.

Upon restarting tipifarnib following a treatment interruption, the cycle and dosing day are to be defined by the following:

- If a dose delay/interruption occurs and resolves within a cycle, dosing picks up where it left off
 - o For example, if a subject's treatment is held on Day 3, subject recovers 14 days later (nominal Day 17 in the cycle) and resumes tipifarnib treatment, the subject is considered to be dosing on Day 3 of the same cycle.
- If the delay goes beyond the cycle (> nominal day 28 of that cycle), upon recovery, the subject should be started at Day 1 of the next cycle.
 - o For example, if a subject's treatment is held on Day 3, subject recovers 30 days later (nominal Day 33 in the cycle) and resumes tipifarnib treatment, the subject is considered to be dosing on Day 1 of the next cycle.

Radiographic imaging for tumor response must maintain the fixed time schedule and is invariant to the drug exposure of the subject. Radiographic imaging will be performed at least once approximately every 8 weeks for 6 months, thereafter once approximately every 12 weeks. All other procedures/visits can follow the cycle's drug administration.

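### Protocol 9.5 gives inconsistent restart doses after related Grade 3 or higher toxicity for subjects already below an earlier dose

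*Protocol*

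**What the plan says.** Protocol 9.5 sets the dose after a hold for related toxicity in its text and again in Table 3, which it introduces as a summary. The term *original dose* occurs three times and is not defined; Table 2 speaks of a starting dose (600 + 600 mg).

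- **Restart, text.** After recovery from Grade 3 or higher hematological or Grade 3 non-hematological toxicity, "tipifarnib may be restarted at the original dose or at the next lower dose level", at the investigator's discretion. For a recurrence: "If grade 3 or 4 toxicity recurs, subsequent dose reductions may be conducted according to Table 2".
- **Restart, Table 3.** For the same event: "restart tipifarnib at current dose or at the next lower dose level (see Table 2) at the judgement of the investigator".
- **Recurrence, Table 3.** The same toxicity leads to the next lower level. The table then adds: "If grade 3 thrombocytopenia recurs, consider additional cycles at original dose at the judgement of the investigator".
- **Re-escalation, text.** Unless otherwise indicated, "reduced doses may be re-escalated to the original dose at the judgement of the investigator".
- **Bar, text.** Subjects with a serious adverse event, or with a recurrence of at least "grade 3 toxicity deemed to be related to tipifarnib will not" "have their dose re-escalated following dose reduction". More than one delay of 14 days or longer also rules out re-escalation.

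Protocol 9.4 explains that the starting dose was 900 mg bid before amendment 5 lowered it to 600 mg bid. Ongoing subjects on 900 mg bid may stay there or switch.

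**The concern.** Where the text says *original* and the table says *current*, a site must choose which to follow, and the choice sets the dose given just after a severe related toxicity. Protocol 9.5 uses *current dose level* elsewhere (in the renal rules), so *original* is not obviously a synonym for it.

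Thrombocytopenia is a relevant toxicity here. Protocol 9.4 reports a Grade 4 event in the first subject, on the earlier 21-day schedule, as one reason for reviewing the regimen. It also reports that reduction to 600 mg lessened toxicity, so a return to 900 mg bid would undo a step taken for tolerability.

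There is a smaller consequence for reporting. SAP 8.2 lists protocol deviations and SAP 8.4 summarises dose increases. Whether a return to 1200 mg/day after recurrent thrombocytopenia counts as a deviation depends on which sentence of 9.5 is applied.

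**Working it through.** **Inputs.** Table 2: start 600 + 600 mg; level -1 300 + 600 mg; level -2 300 + 300 mg. Protocol 9.4: earlier starting dose 900 mg bid. Dosing days per 28-day cycle: days 1-7 and 15-21, so 7 + 7 = 14.

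**Reproducing the plan's figure.** Daily dose = morning + evening. Level -1: 300 + 600 = 900 mg/day, as the Table 2 footnote states. Start: 600 + 600 = 1200. Level -2: 300 + 300 = 600. The steps are 1200 - 900 = 300 and 900 - 600 = 300, matching the 300 mg steps in Protocol 9.4. The earlier start is 900 + 900 = 1800 mg/day.

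**1. Restart sentence against Table 3.** For a subject who began at 600 mg bid and was never reduced, original = current = 1200 mg/day, so there is no difference. The two differ only for a subject now below an earlier dose.

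- *Reduced for toxicity.* A further related Grade 3 or higher event is a recurrence: the text points to reduction and the bar blocks a rise. Reductions for renal or neurological toxicity may not be reversed at all. Almost nobody in this group could be raised, so here the mismatch is mainly one of wording.
- *Switched from 900 to 600 mg bid.* See step 3.

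**2. Recurrent Grade 3 thrombocytopenia in a subject already at level -1.** Per cycle, multiply the daily dose by 14.

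| Rule followed | mg/day | mg per cycle |
|---|---|---|
| Table 3, next lower level | 600 | 600 × 14 = 8,400 |
| Bar on re-escalation | at most 900 | 900 × 14 = 12,600 |
| Table 3 thrombocytopenia line, read as the starting dose | 1200 | 1200 × 14 = 16,800 |

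1200 / 900 = 1.33, a rise of 33% on the current dose; 1200 / 600 = 2, twice the next lower level. For a subject kept at 600 mg bid after the first episode, the bar has nothing to act on: the dose is 1200 mg/day under both rules.

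**3. Subjects who began at 900 mg bid and now take 600 mg bid.** If *original* means the Table 2 start, the ceiling is 1200 mg/day (16,800 mg per cycle). If it means the subject's own first dose, it is 1800 mg/day (1800 × 14 = 25,200 mg per cycle); 1800 / 1200 = 1.5, or 50% more.

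- *For 1200:* Table 2 has no row above 600 + 600, the 9.5 text gives 600 mg bid as everyone's starting dose, and the Table 3 restart line offers nothing above the current dose.
- *Not excluding 1800:* the restart sentence is not limited to any group, and the re-escalation sentence sets no ceiling other than the undefined term. The bar does not stop a return if this is the first related Grade 3 or higher event, no serious adverse event has occurred, and there has been at most one delay of 14 days or longer.

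**The case against.** The strongest reply on thrombocytopenia is that *additional cycles* naturally describes a subject still on that dose. On that view the Table 3 line relaxes the preceding instruction to step down; it permits staying, not rising. The bar applies only after a reduction, so the two rules would not meet. If they did, a mandatory rule in the text could outrank a permissive line in a summary table. This reading is plausible and may be what was intended. It is not what the words say for a reduced subject, and neither passage mentions the other. The line could also be a deliberate exception, but the bar states none.

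On the switched subjects, the reply is largely right: Tables 2 and 3 favour 600 mg bid. A switch under 9.4 is also discretionary and not described as a toxicity reduction, so the re-escalation sentence may not reach it. That leaves the restart sentence, which is not so limited.

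A reader might take the SAP's adverse event tables by starting dose (600 or 900 mg BID; SAP 7.5 and 10.1) as support for 900 mg bid as the original dose. They show only that some subjects began there and give no dosing instruction.

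Numbers are also limited by a further rule: "Asymptomatic laboratory findings will not be considered dose limiting unless otherwise determined by the Investigator". Supportive care, including platelet transfusion, comes before any hold, and nearly every restart or re-escalation choice in dispute is discretionary.

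**Conclusion.** The restart rules in 9.5 are inconsistent for a narrow group. For a reduced subject at level -1 with recurrent Grade 3 thrombocytopenia, the instructions span 600 to 1200 mg/day. For a subject switched from 900 mg bid, the ceiling is probably 1200 mg/day but 1800 is not ruled out. The first result assumes a prior dose reduction and that *original dose* means the Table 2 start; the second assumes that *original* may mean the subject's own first dose.

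Two stronger readings are not supported. Table 3 does not contradict the bar for every recurrent Grade 3 thrombocytopenia, because without a prior reduction the rules agree. Nor does the protocol direct switched subjects back to 1800 mg/day; it only fails to exclude it. That dose is not new to the trial either, since 9.4 lets ongoing subjects stay on it.

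The documents do not give the number affected; it is likely small. The milligram figures describe dose, not measured risk. ORR, alpha and power rest on response counts in 11 and 18 evaluable subjects and do not use these rules. Severity is low.

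**What to change.** 1. In the restart sentence of the 9.5 text, replace *original dose* with *current dose*, to match Table 3.
2. Make the same replacement in the Table 3 thrombocytopenia line, so that it permits staying at the current dose but not re-escalation.
3. State once in 9.5 that, for subjects on or switched to 600 mg bid, re-escalation may not exceed the Table 2 starting dose of 600 mg bid.

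The term then remains only in the re-escalation sentence, with a stated ceiling. A level -1 subject with recurrent Grade 3 thrombocytopenia restarts at 600 or 900 mg/day, and a switched subject cannot exceed 1200 mg/day. Subjects who stay on 900 mg bid under 9.4 keep that permission.

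Marking the Table 3 line as an exception to the bar would be a weaker repair: the undefined term would stay in two places and a reduced subject could still return to 1200 mg/day.

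The cost is slightly less investigator discretion and a short clarification to sites. The statistical design does not change.

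### Table 3 and the text of Protocol Section 9.5 are not consistent on recurrent grade 3 thrombocytopenia after a dose reduction and on first grade 2 renal toxicity, so sites could dose differently depending on which they follow

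*Protocol*

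**What the plan says.** Section 9.5 sets out the dose rules in prose and then presents Table 3 as their summary.

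**Recurrent grade 3 thrombocytopenia.** After a first hematological toxicity of grade 3 or higher that needed a hold, the text lets the investigator restart at the original dose or one level lower. If grade 3 or 4 toxicity recurs, further reductions are allowed but not required. Later the text permits re-escalation in general and then limits it: subjects with a serious adverse event, or with a recurrence of at least "grade 3 toxicity deemed to be related to tipifarnib will not" have a reduced dose raised again. Table 3, in the row for the same toxicities, directs the next lower level when a toxicity recurs and then adds: "If grade 3 thrombocytopenia recurs, consider additional cycles at original dose at the judgement of the investigator".

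**First grade 2 renal toxicity.** The text applies when "treatment-related treatment-emerging CTCAE grade 2 renal toxicity is observed that cannot be managed with supportive care measures". It then gives the action ("abnormalities, if appropriate), treatment with tipifarnib will be interrupted until recovery to" grade 1 or better) and the restart ("the subject may restart tipifarnib at their current dose level"). The Grade 2 Renal row of Table 3 has two cells. The management cell reads "Manage with BSC, including hydration and correction of electrolyte abnormalities, if appropriate". The dosing cell says that on recovery to grade 1 or better the site should "restart tipifarnib at current dose". The row below, for recurrent grade 2 or grade 3 renal toxicity, opens with the same management sentence and then adds the hold for cases that supportive care does not control.

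**The concern.** A site that reads only the table and a site that reads only the text could reach different dosing decisions for the same subject. A subject reduced after a first platelet event could be taken back up where the text forbids it. A subject with a first grade 2 renal toxicity not controlled by supportive care could stay on drug where the text interrupts it, because the contrast with the next row invites the inference that the hold applies only to recurrent grade 2 or grade 3.

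The protocol itself treats both toxicities as relevant. The notes to Table 1 name creatinine elevations as a described effect and add a Day 7 chemistry test. Section 9.4 gives grade 4 thrombocytopenia, in a subject on the earlier 21-day schedule, as one reason for reviewing the regimen. Subject safety is the main stake. There is also a data consequence: one decision could be compliant under the table and a deviation under the text, or the reverse.

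**Working it through.** There is no sample size, power or alpha figure to reproduce. The check sets the text beside the table.

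**1. Recurrent grade 3 thrombocytopenia**

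| Subject's history | Text | Table 3 | Result |
|---|---|---|---|
| Restarted at the unreduced dose, then recurs | Reduction optional; staying at the same dose is not re-escalation | Next lower level, or consider *original dose* | Compatible |
| Reduced after the first event, then recurs | No re-escalation | Next lower level, or consider *original dose* | Conflict, if *original dose* means the dose before reduction |

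Size of the gap, from Table 2 (morning plus evening dose):

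- Starting dose: 600 + 600 = 1200 mg a day.
- Level -1: 300 + 600 = 900 mg a day. Return to the starting dose adds 300 mg, and 300/900 = 33%.
- Level -2: 300 + 300 = 600 mg a day. Return to the starting dose adds 600 mg, and 600/600 = 100%.

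The meaning of *original dose* decides the matter, and Section 9.5 does not settle it:

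- For the first restart, the text says *original dose* where the table says *current dose*. If the two terms are interchangeable, the table's sentence permits no re-escalation and the conflict disappears.
- In the general permission to re-escalate, the text uses *original dose* for the level held before a reduction. On that usage the conflict stands.
- Section 9.4 lets ongoing subjects stay on 900 mg bid. For them the original dose need not be the starting dose in Table 2.

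**2. First grade 2 renal toxicity**

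| Element | Text | Table 3, Grade 2 Renal row | Table 3, next row |
|---|---|---|---|
| Trigger: not controlled by supportive care | Stated | Absent | Stated |
| Interruption | Stated | Absent; implied only by *restart* | Stated |
| Recovery to grade 1 or better | Stated | Stated | Stated |
| Restart dose | Current level | Current dose | Next lower level |

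Two of the four elements are missing from the row. The two that are present agree with the text. The management sentence is common to both renal rows, so the gap shows only when they are compared.

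**3. Precedence and effect on the analysis**

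Section 9.5 does not say whether text or table governs. SAP Section 8.2 lists protocol deviations, Section 6 removes major deviations from the Per-Protocol population, and Section 8.4 summarises dose intensity and dose modifications. These are supportive or descriptive uses. The primary response analysis uses the Full Analysis Set, and the 11 + 7 design does not depend on either row.

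**The case against.** The strongest case is that a summary table may abbreviate and that the full rules stand in the same section.

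- **Renal.** *Restart* presupposes a hold, the recovery threshold and restart dose match the text, and following the text breaches nothing in the table. This stands: the point is an omission. A reader might infer that the table tells sites to keep dosing; it does not. But a word that implies a hold does not say when to hold, and that is what the text specifies.
- **Thrombocytopenia.** The bar applies only after a dose reduction, so there is no conflict for subjects who restarted at the unreduced dose. This stands, and so does the point that *original dose* may mean *current dose*.
- **Opposite instructions.** A reader might infer these. The documents do not support it: the table only asks the investigator to consider the option, and an investigator who leaves the dose reduced complies with both.
- **Other sentences in Section 9.5.** Laboratory findings without symptoms are not dose limiting unless the investigator decides otherwise. That may make both situations rarer, but the bar turns on recurrence of related toxicity, not on whether it is dose limiting. The qualifier that opens the re-escalation paragraph limits the permission to re-escalate, not the bar that follows.
- **Detection.** Section 10.14.2 requires chemistry and microscopic urinalysis when creatinine reaches grade 2. That finds the event; it does not settle the action.
- **Earlier data.** In the leukemia study described in Section 9.4, the dose-limiting rising grade 2 creatinine occurred at 1400 and 1600 mg bid, and grade 3 creatinine in 1 of 6 patients at 1200 mg bid. This trial starts at 600 mg bid, so those findings give no rate for it.

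**Conclusion.** The inconsistency is real and narrow: two of the six rows of Table 3. In one, the table permits a re-escalation that the text forbids. This is limited to subjects already reduced and assumes that *original dose* means the dose before reduction; on Table 2 the difference is then 300 or 600 mg a day. In the other, the table leaves out the interruption and its trigger, assuming the row's cells are complete; both end in full sentences.

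Sites could dose differently. A reader might go further and say that they will, but the documents do not say which source sites use, and they give no count of affected subjects. This should be corrected because it concerns safety and costs almost nothing. It is a matter of internal consistency and leaves the response endpoint, the sample size and the two-stage figures unaffected.

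**What to change.** Reconcile Table 3 with the Section 9.5 text on three matters:

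1. whether recurrent grade 3 thrombocytopenia is an exception to the bar on re-escalation for subjects already reduced;
2. what *original dose* means, including for subjects who began at 900 mg bid, with one term used in both places;
3. whether and when a first grade 2 renal toxicity interrupts treatment, stated alike in text and table.

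Add a sentence saying whether text or table governs if they differ. Each clinical rule is for the sponsor to decide. The cost is two table cells or two sentences, plus the definition and the precedence statement; no analysis changes. If dosing has already taken place under both readings, the memorandum that fixes the Per-Protocol population should say how such cases were classified.
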